9.2.3 International Index of Erectile Function Questionnaire

The 15-question IIEF Questionnaire is a validated, multi-dimensional, self-administered investigation that has been found useful in the clinical assessment of erectile dysfunction and treatment outcomes in clinical trials (Rosen et al., 1997). A score of 0-5 is awarded to each of the 15 questions that examine the 5 main dimensions of male sexual function: erectile function, orgasmic function, sexual desire, intercourse satisfaction and overall satisfaction ([Appendix 5. International Index of Erectile Function Questionnaire](#)). The entire questionnaire will be administered to the subject, however, only the first 5 questions associated with the Erectile Function domain will be used for the efficacy assessments.

This information will be collected at Visits 2, 3, 4, ET (if needed), and at the Off-Treatment Safety Follow-up Visit.

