2.2.13.3 Secondary Endpoints

P values for secondary endpoints will be used for descriptive purposes rather than for statistical inference; therefore, no adjustments for multiplicity will be utilized.

The following four change from Baseline to Week 12 endpoints will be analyzed in a manner similar to the primary efficacy analysis as described in Section 2.2.13.1:

- (1) NIH-CPSI pain subscale (pain, urinary symptoms and quality of life impact) and all domains total score
 - Total score (score range 0-43)
 - Pain: Total of items 1a, 1b, 1c, 2a, 2b, 3, 4 (score range 0-21)
 - Urinary Symptoms: total of items 5 and 6 (score range 0-10)
 - QoL Impact: total of items 7,8 and 9 (score range 0-12)

NIH-CPSI data are collected on a paper form at each planned clinic visit.

- (2) Male sexual health as measured using the International Index of Erectile Function Questionnaire, Erectile Function domain (IIEF-EF): The IIEF-EF score is the sum of the ordinal responses to the 5 items

IIEF-EF data are collected on a paper form at each planned clinic visit.

- (3) Mean of average daily pelvic pain scores (eDiary), average pelvic pain (in clinic), and maximum daily pelvic pain (in clinic).

Average and maximum daily pelvic pain are collected on the eDiary, and also on a paper form at each planned clinic visit. Analysis of data collected on paper at the planned clinic visits will be used to confirm results from the analysis of data collected on the eDiary.

- (4) 24-hour voiding frequency

For each of the scheduled assessment periods, the voiding frequency will be the last 24-hour period in which voiding is collected (i.e., if voiding is collected in more than one 24-hour period).

The following four-time course secondary endpoints will be assessed by MMRM model where the change from Baseline (Visit 2) to Week 6 (Visit 3), Week 12 (Visit 4), and Week 16 (i.e. 4 weeks after end of treatment) is the dependent variable:

- (1) Mean of maximum daily pelvic pain score (eDiary)
- (2) NIH-CPSI pain subscale and all domains total score
- (3) IIEF-EF
- (4) Mean of average daily pelvic pain scores (eDiary), average and maximum pelvic pain (Paper-based NRS in clinic)

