 - Decrease in maximum daily pelvic pain (mean) from Baseline to Week 12 using a standardized 11-point NRS with no change in the amount or strength of concomitant analgesic medications (as defined in Section 2.2.14).
 - Decrease in maximum daily pelvic pain from Baseline to Week 12 using a standardized 11-point NRS with a decrease in the amount or strength of concomitant analgesic medications (as defined in Section 2.2.14).
- (2) A $\geq 30\%$ and $\geq 50\%$ improvement (decrease) in maximum daily pelvic pain (mean) (using the 11-point NRS recorded by eDiary and the NIH-CPSI pain subscale), at Weeks 6 (Visit 3) and 12 (Visit 4).

For the Discontinuation of study medication due to treatment failure endpoint, only summary statistics will be provided for the percent meeting treatment failure criteria and the time to event (no inferential analyses will be performed). Time to discontinuation of study medication due to treatment failure will be summarized and presented graphically using Kaplan-Meier methods (i.e., SAS PROC LIFETEST stratifying on treatment group).

The frequency distribution of the 5-category IIEF-EF score will be presented by treatment group for Week 12 as well as a shift table from Baseline. The 5 categories are no erectile dysfunction (score: 26-30), mild erectile dysfunction (score: 22-25), mild to moderate erectile dysfunction (score: 17-21), moderate erectile dysfunction (score: 11-16) and severe erectile dysfunction (score: 1-10). Responses to all items must be completed to calculate an IIEF-EF score. Any response with missing values will be excluded from the analyses. Treatment group difference

with corresponding 95% CIs in the 5-category IIEF-EF will be assessed by a Cochran-Mantel-Haenszel (CMH) test using row mean scores controlling for Baseline IIEF-EF score.

Data from both treatment arms will be used to calculate a meaningful change threshold (MCT), which reports a change in the primary endpoint (change in maximum daily pelvic pain) by anchoring to other outcomes (including PGI-S and/or PGI-C) to determine a change in maximum pelvic pain that provides a meaningful benefit to patients. The determination of the MCT will be made outside of the methods documented in this SAP prior to database lock. Once the MCT is determined, the proportion of subjects who have an improvement of at least the MCT will be summarized by treatment group and compared using a chi-square test as an exploratory analysis.

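### The IIEF-EF score is a sum of five items scored 0-5 (range 0-25), but its severity cut-offs run from 1 to 30, so the category for no erectile dysfunction (26-30) cannot be reached

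*SAP*

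**What the plan says.** Protocol 9.2.3 sets the item range: "A score of 0-5 is awarded to each of the 15 questions". It then limits which items count: "only the first 5 questions associated with the Erectile Function domain will be used for the efficacy assessments". SAP 2.2.13.3, item (2) in the list of change endpoints, gives the scoring rule: "The IIEF-EF score is the sum of the ordinal responses to the 5 items".

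Later in the same SAP section the score is cut into categories: "The 5 categories are no erectile dysfunction (score: 26-30), mild erectile dysfunction (score: 22-25"), then mild to moderate at 17-21, then "moderate erectile dysfunction (score: 11-16) and severe erectile dysfunction (score: 1-10"). On incomplete forms the rule is "Responses to all items must be completed to calculate an IIEF-EF score".

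The categories feed three outputs: a Week 12 frequency distribution by arm, a shift table from Baseline, and a CMH "test using row mean scores controlling for Baseline IIEF-EF score". Protocol 10.4.2.5 asks for the same category analyses and refers to Appendix 5 for the five categories. The Appendix 5 text available for this review shows the questions and response options, but neither categories nor numeric codes.

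**The concern.** The scoring rule and the cut-offs describe scales of different length. If the plan is followed exactly, the table must show 0% of men without erectile dysfunction in both arms, whatever the data. A man who gives the best possible answer to every scored item is labelled as having mild dysfunction, and no shift into or out of the top category can appear. Male sexual health, measured by IIEF-EF, is a named secondary objective, so these tables would make a false clinical statement about the trial population.

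At the other end, a man who scores 0 on all five items has a complete form but no category.

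**Working it through.** **Inputs**
- Items scored: 5 (Protocol 9.2.3; SAP 2.2.13.3).
- Range per item: 0 to 5 (Protocol 9.2.3; the SAP gives no item range).
- Bands: 26-30 none, 22-25 mild, 17-21 mild to moderate, 11-16 moderate, 1-10 severe (SAP 2.2.13.3).

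**Step 1: try to reproduce the span of the bands.** Together the bands cover 1 to 30.
- Highest total = 5 × 5 = 25, below 26.
- Lowest total = 5 × 0 = 0, below 1.

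The 1-30 span is not reproduced at either end.

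**Step 2: place each of the 26 possible totals (0 to 25).**

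| Band | Limits | Reachable totals |
|---|---|---|
| None | 26-30 | 0 |
| Mild | 22-25 | 4 |
| Mild to moderate | 17-21 | 5 |
| Moderate | 11-16 | 6 |
| Severe | 1-10 | 10 |
| No band | 0 | 1 |

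Check: 0 + 4 + 5 + 6 + 10 + 1 = 26. All five values of the top band are out of reach.

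**Step 3: see whether another coding or item list removes the conflict.**

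| Variant | Range | Top band reachable? | Total without a band | Fits the text? |
|---|---|---|---|---|
| 5 items, 0-5 | 0-25 | No | 0 | Yes; this is the plan |
| 5 items, 1-5 | 5-25 | No | none | No (item range) |
| 5 items, 1-6 | 5-30 | Yes | none | No (item range) |
| 6 items, 0-5 | 0-30 | Yes | 0 | No (item count) |
| Items 1-5 at 0-5, plus question 15 at 1-5 | 1-30 | Yes | none | No (item count) |

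No variant both fits the documents and makes the top band reachable. The last row matches 1-30 exactly. Question 15 also asks about erections, and Appendix 5 gives it five response options with no option for no activity. This points to a slip in the item count, but it is an inference; neither document says so.

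**Step 4: trace what uses the bands.** Only the Week 12 distribution, the shift table and the CMH row-mean test do. The Week 12 change and time-course analyses use the sum itself.

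**The case against.** The best defence has four parts.

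1. *The 0-25 range rests on one general protocol sentence.* That sentence covers all 15 questions and is loose: questions 11 to 15 list only five response options. This is fair, but it does not help the plan. Questions 1 to 5 each print six options, which fits 0-5. The only five-item coding tried that reaches 30 is 1-6, and it contradicts that sentence.

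2. *The missing piece may be in Appendix 5.* Protocol 10.4.2.5 points there for the categories, and the text available may be incomplete. So the statement that no rescaling or sixth item is given applies only to the text available. Whatever the appendix holds, the five-item rule in both documents still conflicts with the cut-offs printed in the SAP.

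3. *The score of 0 may not be a second defect.* This stands. If the key turns out to be items 1 to 5 at 0-5 plus question 15 at 1-5, a total of 0 cannot occur. A reader might infer that men scoring 0 at Week 12 would be dropped, an exclusion based on an outcome after randomization. The documents do not support that: the SAP excludes forms with missing values, and a 0 is not missing. Dropping such men is one possible programming result; placing them in the severe band is another. How often 0 would occur cannot be estimated.

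4. *An empty top category does not invalidate a CMH row-mean test.* This also stands. The same scoring applies to both arms, and a reader who infers bias between arms would go beyond what can be shown. What is lost is correct labelling and a category at the top of the scale.

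Two other inferences are tempting. One is that the five-item change score is wrong; without the scoring key this is not shown. The other is that item 5 would be mis-scored because, after its first option, its answers run from worst to best while those of items 1 to 4 run from best to worst. No coding error is shown; the numeric codes are simply a detail that the plan leaves out.

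**Conclusion.** The plan is wrong as written and should be corrected. Under its own rules, 0 of the 26 possible totals fall in the category for no erectile dysfunction, the best possible total of 25 is reported as mild, and one total (0) has no category.

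This rests on two statements in the documents: items scored 0-5, and only five of them used. It also rests on there being no rescaling elsewhere, which can be confirmed only for the text available.

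The consequence is narrow. It touches the Week 12 frequency table, the shift table and one CMH test. The SAP treats secondary P values as descriptive. The primary endpoint, the sample size and the safety analyses do not depend on IIEF-EF.

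**What to change.** Act before the interim freeze/lock and unblinding that SAP 2.2.12 places after the last Week 16 visit, because choosing items or cut-offs afterwards would be a post-hoc scoring decision. Check the instrument's scoring key and make the item list, the numeric item codes and the cut-offs agree. Then take one of two routes:

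- **(a) If the key's domain has more than five items:** amend Protocol 9.2.3 and SAP 2.2.13.3, and use the resulting score in every IIEF-EF analysis (Week 12 change, time course, categories, shift table and CMH test).
- **(b) If the five-item sum is kept:** replace the SAP cut-offs with ones made for a 0-25 range.

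If a total of 0 is still possible after this, assign it to a category.

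**Cost.** No new data under either route, since "The entire questionnaire will be administered to the subject". Route (a) needs a protocol amendment and a SAP revision, and it changes the score behind two listed secondary endpoints (Week 12 change and time course). Route (b) needs a SAP revision only and changes just the category outputs.

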10.4.2.5 Secondary Efficacy Endpoints Analyses

For the following dichotomous secondary efficacy endpoints, the rates for each treatment group and the difference between the treatment groups will be presented with corresponding 95% CIs. A Cochran–Mantel–Haenszel test will be used to test for differences in rates between the treatment groups controlling for baseline pelvic pain.

- Treatment response as defined by meeting either of the following:
 - Decrease in maximum daily pelvic pain from Baseline to Week 12 using a standardized 11-point NRS with no change in the amount or strength of concomitant analgesic medications
 - Decrease in maximum daily pelvic pain from Baseline to Week 12 using a standardized 11-point NRS with a decrease in the amount or strength of concomitant analgesic medications
- A $\geq 30\%$ and $\geq 50\%$ improvement in maximum daily pelvic pain (using the 11-point NRS recorded by eDiary and the NIH-CPSI pain subscale), at Weeks 6 (Visit 3) and 12 (Visit 4).
- Discontinuation of study medication due to treatment failure (% meeting treatment failure criteria and time to event)

The following change from Baseline to Week 12 endpoints will be analyzed in a manner similar to the primary efficacy analysis as described in [Section 10.4.2.3](#).

- NIH-CPSI pain subscale and all domains total score.
- Male sexual health as measured using the IIEF-EF.
- Mean of average daily pelvic pain scores (eDiary), daily pelvic pain (in clinic), and maximum daily pelvic pain (in clinic).
- 24-hour voiding frequency

Additionally, for the IIEF-EF domain endpoint, the frequency distribution of the 5 category IIEF-EF score (i.e. described in [Appendix 5. International Index of Erectile Function Questionnaire](#)) will be presented by treatment group for Week 12 as well as a shift table from Baseline. Treatment group difference in the 5-category IIEF-EF will be assessed by a Cochran-Mantel-Haenszel (CMH) test controlling for Baseline IIEF-EF score.

The following time course secondary endpoints will be assessed by MMRM ANCOVA model where the change from Baseline is the dependent variable and linear trends across time (i.e., visit) are assessed.

Time course of effects: AQX-1125 (200 mg once-daily) compared to placebo on the change from Baseline (Visit 2) to Week 6 (Visit 3), Week 12 (Visit 4) and Week 16 (i.e. 4 weeks after end of treatment) for each of the following:

- Mean of maximum daily pelvic pain score (eDiary).

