- The change from Baseline to Week 12 for each of the following:
 - NIH-CPSI pain subscale and all domains total score
 - Male sexual health as measured using the IIEF-EF
 - Mean of average daily pelvic pain scores (eDiary), average and maximum pelvic pain (Paper-based NRS in clinic)
 - 24-hour voiding frequency (eDiary)
- Time course of effects: AQX-1125 (200 mg once-daily) compared to placebo on the change from Baseline (Visit 2) to Week 6 (Visit 3), Week 12 (Visit 4), and Week 16 (i.e. 4 weeks after end of treatment) for each of the following:
 - Mean of maximum daily pelvic pain score (eDiary)
 - NIH-CPSI pain subscale and all domains total score
 - IIEF-EF
 - Mean of average daily pelvic pain scores (eDiary), average and maximum pelvic pain (Paper-based NRS in clinic)
 - 24-hour voiding frequency (eDiary)
- Response to treatment compared to placebo as measured by the GRA, PGI-C, and PGI-S at Week 12 (Visit 4)
- A $\geq 30\%$ and $\geq 50\%$ improvement in maximum daily pelvic pain (using the 11-point NRS recorded by eDiary and the NIH-CPSI pain subscale) compared to placebo, at Week 6 (Visit 3) and Week 12 (Visit 4)
- Responder analysis: Response to treatment defined by any of the following:
 - Decrease in maximum daily pelvic pain from Baseline to Week 12 (eDiary) with no change in the amount or strength of concomitant analgesic medications
 - Decrease in maximum daily pelvic pain from Baseline to Week 12 (eDiary) with a decrease in the amount or strength of concomitant analgesic medications
- Discontinuation of study medication due to treatment failure (% meeting treatment failure criteria and time to event)

Safety Endpoints

The safety endpoints are:

- The frequency and severity of AEs will be reported for the treatment phase and will include:
 - Abnormal, clinically significant vital signs, laboratory tests, electrocardiogram (ECG), weight or findings on physical examinations
 - Ophthalmic safety based upon assessment of lenticular opacification using LOCS III, BCVA using the LogMar chart, IOP, corneal staining and slit lamp examination at Baseline, 12 weeks, and 6 months post last dose, and at Early Termination (ET).

Statistical Methods:

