Subject pelvic pain as assessed by the 11-point NRS (eDiary) will be summarized at each week during the study. Analyses in the week prior to the Week 6 Visit, Week 12 Visit and Week 16 Visit (Off-Treatment Safety Follow-Up) will be produced with mean, median, standard deviation, and quartiles for both pelvic pain score and the change from baseline in pelvic pain score, using the mean of the maximum observed value from each of the 7 days prior to each visit (Baseline, Week 6, Week 12 and Week 16). This will be reported for maximum daily pelvic pain score and similarly for average daily pelvic pain score. The proportion of subjects who respond to treatment at Week 6, Week 12 and at Week 16 will be summarized. Use of concomitant analgesic medication will be summarized with the percentage (%) of subjects taking each class of medication (permitted short-acting opioid-containing analgesics and non-opioid containing analgesics: e.g., acetaminophen) and the daily dose (mean, median, standard deviation, and quartiles, using subjects who took any such medication on at least 1 of the 7 days prior to the Baseline, Week 6, Week 12 or Week 16 Visit).

Other secondary endpoints will be summarized at Baseline, Week 6, Week 12, and Week 16, including observed values at each timepoint and change from Baseline at post-baseline timepoints, with mean, median, standard deviation, and quartiles for continuous data, and counts and percentages for categorical and binary data.

Comparison of AQX-1125 to placebo at Week 12 for the primary efficacy endpoint will use repeated measures analysis of variance to compare change from Baseline in maximum pain score (NRS score) (dependent variable) between treatment arms (AQX-1125 and placebo). Baseline

maximum pain score (NRS score) will be included in the model as a covariate. Change from Baseline to Week 6 and Week 12 will be included in the analysis. A P value less than or equal to 0.05 for the change from Baseline at Week 12 will be considered statistically significant. All randomized subjects will be included in the primary analysis.

Comparison of AQX-1125 to placebo for proportion of subjects who are responders will be used to further understand the effect of AQX-1125 on pelvic pain. P values for the test of equal numbers of responders in each group will be reported, without adjustment for multiplicity, and used descriptively.

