2.2.13.1 Primary Endpoint

The primary endpoint is the change from Baseline (Visit 2) to Week 12 (Visit 4) in the maximum daily pelvic pain (mean) using a standardized 11-point numerical rating scale (NRS) pain score recorded daily by an eDiary.

Average maximum pain scores will be summarized by week for each of the planned 12 weeks of treatment, for each treatment group. The results will be reported in a table and also graphically.

The primary analysis will use data from week 6 and week 12, based on actual clinic visit dates. If a subject has at least 4 recorded maximum pelvic pain scores in the 7 days prior to a clinic visit, the mean of the available scores will be calculated to be that subject’s value in the primary efficacy analysis. These values will differ slightly from the weekly reported pain score, if a subject’s clinic visit is not on the exact target date.

Comparison of AQX-1125 to placebo at Week 12 for the primary efficacy endpoint will use MMRM. SAS PROC MIXED will be used with the observed change from baseline score at Week 6 and Week 12 as dependent variables. The model will include the baseline NRS score as a fixed effect covariate with fixed effect categorical factors for treatment group, visit and baseline×visit and treatment×visit interactions. The interactions will remain in the model regardless of significance. Treatment group comparisons at each visit (including the primary analysis endpoint at the Week 12 visit) will be estimated by least squares (LS) means differences with accompanying p-values and 95% CIs.

An unstructured covariance pattern will be used to estimate the variance–covariance of the within-subject repeated measures. Sample SAS code for the primary efficacy endpoint analysis is provided in Appendix B – Sample MMRM Code.

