The MMRM model to assess time course will have treatment as a factor, the corresponding baseline value as a covariate, a linear term for time (in weeks), and a time×treatment interaction effect term. The model will allow for a subject random intercept and slope over time with an unstructured correlation matrix. Sample SAS code for the time course MMRM is provided in Appendix B – Sample MMRM Code.

For response to treatment as measured by the GRA and PGI-C at Week 12 (Visit 4), the frequency distribution of each response scale will be presented by treatment group and assessed using a chi-square row mean score difference test.

- The GRA response is a 7-point Likert scale (range: -3 to 3) with a score of -3 indicating “Markedly Worse”, a score of 0 indicating “No Change”, and a score of 3 indicating “Markedly Improved” to the question: *As compared to when you started the study drug, how would you rate your Chronic Prostatitis / Chronic Pelvic Pain Syndrome symptoms now?*
- The PGI-C response is a 7-point Likert scale (range: 1 to 7) with a score of 1 indicating “Very much improved”, a score of 4 indicating “No change”, and a score of 7 indicating “Very much worse” to the item: *Choose the response that best describes the overall change your pelvic pain since you started the study.*
- The PGI-S response is a 5-point ordinal scale with a score of 1 being “None” and a score of 5 being “Very Severe” to the item: *Choose the response that best described the severity of your chronic prostatitis / chronic pelvic pain symptoms over the past week.*

For response to treatment as measured by the PGI-S at Week 12 (Visit 4), the frequency distribution of each response scale will be presented by treatment group and the change from baseline will be assessed by an ANCOVA model with treatment as a factor and baseline PGI-S as a covariate.

For the following two dichotomous secondary efficacy endpoints the rates for each treatment group and difference between the treatment groups will be presented with corresponding 95% CIs. A CMH test will be used to test for differences in rates between the treatment groups controlling for baseline pelvic pain. The baseline pelvic pain will be stratified into 2 categories (4-7 and >7):

- (1) Treatment response as defined by meeting either of the following:

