Appendix B – Sample MMRM Code

The following is sample SAS Proc Mixed code to be used for the primary endpoint analysis.

```
**-----**;  
** usubjid: subject identifier **;  
** visit: visit identifier **;  
** trt: treatment identified **;  
** chg: change from baseline value **;  
** base: baseline value **;  
  
proc mixed data=xxxx;  
  class usubjid visit trt(ref='0');  
  model chg = base visit trt base*visit trt*visit/s;  
  repeated /subject=usubjid type=un;  
  ** note: LS Mean analysis is primary analysis **;  
  lsmeans trt trt*visit / diff cl;  
  ods output LSMeans=LSMeans DiffS=diffs;  
  where visit >0;  
run;
```

The following is sample SAS Proc Mixed code for the MMRM to assess time course

```
**-----**;  
** usubjid: subject identifier **;  
** visit: visit identifier (numeric) **;  
** trt: treatment identified **;  
** chg: change from baseline value **;  
** base: baseline value **;  
  
proc mixed data=xxxx;  
  class usubjid trt(ref='0');  
  model chg = base visit trt trt*visit/s;  
  random intercept visit /subject=usubjid type=un;  
  where visit >0;  
run;
```

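### The time-course model puts Week 16 (off drug) on the same straight line as Weeks 6 and 12 (on drug), so the Week 16 comparison has no free estimate and the slope mixes on-drug with off-drug change

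*SAP*

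**What the plan says.** **Endpoint.** Protocol 10.4.2.4 and the SAP synopsis define the time course as the drug-placebo comparison on change from Baseline at Weeks 6, 12 and 16.

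**Model.** SAP 2.2.13.3 puts all three changes into one mixed model, including the off-drug one: "Week 16 (i.e. 4 weeks after end of treatment) is the dependent variable". The model "will have treatment as a factor, the corresponding baseline value as a covariate, a linear term for time (in weeks"), together with a time by treatment interaction and a random intercept and slope per subject. The sample code in SAP Appendix B is "model chg = base visit trt trt*visit/s". Visit is not in the CLASS statement and is described as "visit: visit identifier (numeric"). The block contains no LSMEANS or ESTIMATE statement. Protocol 10.4.2.5 plans the same kind of analysis: "linear trends across time (i.e., visit) are assessed".

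**Other analyses of the same outcomes.** The primary model (SAP 2.2.13.1) treats visit as a factor and yields "Treatment group comparisons at each visit (including the primary analysis endpoint at the Week 12 visit"), but it uses Weeks 6 and 12 only. SAP 2.2.13.3 extends it to the change-to-Week-12 secondary endpoints. The daily-value analysis in SAP 2.2.13.2 ends at day 84. For Week 16 the synopsis plans summaries: "Other secondary endpoints will be summarized at Baseline, Week 6, Week 12, and Week 16".

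**Endpoint list.** The SAP synopsis includes "24-hour voiding frequency (eDiary") among the time-course endpoints, as do Protocol 10.4.2.4 and 10.4.2.5. The list of four time-course endpoints in SAP 2.2.13.3 leaves it out.

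**The concern.** The endpoint asks for three comparisons, the last of them off drug. The model gives each arm its own intercept and slope, so the between-arm difference is itself a straight line in time. A line cannot bend at Week 12, which is where an off-drug change would start. The random slopes do not help, because each subject's path is also linear.

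Readers would get Week 16 summaries by arm and a slope that cannot separate gain on drug from loss off drug. Depending on the true course, that slope may be right, flatten a rise and fall to almost nothing, or point the opposite way from the on-drug change. The mismatch between endpoint and method is in both documents, because the linear trend comes from the protocol.

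**Working it through.** **Inputs.** Times 6, 12 and 16 weeks (SAP 2.2.13.3). Difference 1.2 points, SD 2.0, 45 per arm, 2-sided 5% (Protocol 10.2). The Week 6 and Week 16 differences, the within-subject correlation, and 45 per arm with SD 2.0 at Week 16 are assumptions; the documents give no off-drug course.

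**Plan's own figure.** A two-sample t-test with difference 1.2 and SD 2.0 has power 0.795 at 44 per arm and 0.804 at 45. Then 90/(1 - 0.10) = 100. The stated sample size reproduces and is not in dispute.

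**Slope weights, no profile assumed.** With complete data and a random intercept and slope on the same time variable, the generalised least-squares coefficients equal ordinary least squares. Mean time = (6 + 12 + 16)/3 = 11.333. Sxx = 28.444 + 0.444 + 21.778 = 50.667. Each weight is (t - 11.333)/Sxx:

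- Week 6: -5.333/50.667 = -0.105
- Week 12: 0.667/50.667 = +0.013
- Week 16: 4.667/50.667 = +0.092

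A 1.2-point effect at one visit alone moves the slope by 0.126 per week if it occurs at Week 6, 0.111 at Week 16, and 0.016 at Week 12.

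The fitted Week 16 difference is -0.158 d6 + 0.395 d12 + 0.763 d16, where d6, d12 and d16 are the true differences. It borrows from the on-drug visits.

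**Assumed profiles (drug minus placebo; -1.2 at Week 12 is the plan's figure).**

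| True difference, Weeks 6/12/16 | Slope per week | Fitted line, Weeks 6/12/16 |
|---|---|---|
| -1.2/-1.2/-1.2 | 0 | exact |
| -0.6/-1.2/-1.6 | -0.100 | exact |
| -0.6/-1.2/-1.2 | -0.063 | -0.66/-1.04/-1.29 |
| -0.6/-1.2/-0.6 | -0.008 | -0.76/-0.81/-0.84 |
| -0.8/-1.2/0 | +0.068 | -1.03/-0.62/-0.35 |
| -1.2/-1.2/0 | +0.111 | -1.39/-0.73/-0.28 |

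For row five the slope is (-0.105)(-0.8) + (0.013)(-1.2) + (0.092)(0) = +0.068 with unrounded weights. It reads as steady waning, although the effect grew on drug.

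In the last row the on-drug slope is zero. With equal correlation r between visits, the slope's standard error is 2.0 x sqrt((1 - r)/50.667) x sqrt(2/45), which is 0.050, 0.042 and 0.032 for r = 0.3, 0.5 and 0.7. The slope would then reach P < 0.05 in about 61%, 75% and 93% of trials. A simulation of the SAP model for this row (60 trials, r = 0.5) averaged -1.31/-0.70/-0.29 with slope 0.10, within two Monte Carlo standard errors of the formula.

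**Time coding.** If visits were coded 3, 4, 5 (an assumed numbering, since the Week 16 visit has none), the weights become -0.5, 0 and +0.5. Week 12 then drops out of the slope, and the linear profile -0.6/-1.2/-1.6 is no longer fitted exactly (-0.63/-1.13/-1.63).

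**What a free estimate would give.** Week 16 difference, 95% half-width: t(88) x 2.0 x sqrt(2/45) = 0.84. For the Week 16 minus Week 12 contrast, multiply by sqrt(2(1 - r)): 0.84 at r = 0.5 and 0.53 at r = 0.8.

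**The case against.** The strongest reply is that the protocol itself specified a linear trend and the SAP follows it. A trend is a legitimate, coarse summary, and constant or linear courses are not distorted. Secondary P values are descriptive. A rise and fall would be visible in the Week 16 summaries set beside the Week 6 and 12 estimates, and anyone could form an unadjusted Week 16 interval from the tabulated n, mean and SD. The synopsis also says other secondary endpoints will be tested by an analogous procedure. Neither document asks for a Week 16 minus Week 12 contrast, and the Appendix B code is only a sample.

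Much of this limits the stakes, and some of it stands. The Week 16 data are not lost, the 0.84 half-width is that of a plain two-sample interval, and the distorted cases rest on assumed profiles. The contrast is an addition; it is proposed because it isolates the off-drug change. For subjects who stop drug early, the off-treatment visit is timed from the last dose and may not fall at Week 16.

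The core point is not answered. The general synopsis sentence does not override the specific model in 2.2.13.3. The fixed-effect solution also prints a treatment coefficient, but that is the difference extrapolated to time zero, and any Week 16 value derived from it lies on the constrained line. A reader's own interval from summary tables is not a planned, baseline-adjusted comparison and cannot give the within-subject contrast.

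**Conclusion.** The concern holds. A named secondary comparison, Week 16 against placebo, has no planned unconstrained estimate with a confidence interval, and the planned slope is close to a Week 16 minus Week 6 contrast. The weights need only complete data at Weeks 6, 12 and 16. The size of any distortion depends on the unknown off-drug course: none if the differences lie on a straight line, and a hidden turning point or a reversed sign otherwise.

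The stakes are minor to moderate. The primary analysis, the Week 12 secondary results, power and type I error are untouched. Two smaller points also stand: the text and the sample code describe the time variable differently, and 24-hour voiding frequency has no model that includes Week 16.

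**What to change.** Amend SAP 2.2.13.3 and Appendix B before unblinding, and record the departure from Protocol 10.4.2.5:

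- Fit change at Weeks 6, 12 and 16 with visit in CLASS, treatment by visit, baseline by visit, and a 3 x 3 unstructured covariance.
- Report the LS-mean difference with 95% CI at each visit, and a between-arm Week 16 minus Week 12 contrast.
- State how off-treatment visits of subjects who stopped drug early are assigned to Week 16.
- Keep the linear trend as supplementary if wanted, with time coded 6, 12, 16 in weeks.
- Put 24-hour voiding frequency back in the time-course list.

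The cost is SAP wording and a few lines of code; the data are already being collected. Each model has 9 fixed effects (6 arm-by-visit means, 3 baseline slopes) instead of 5 (intercept, baseline, time, treatment, time by treatment). It has 6 covariance parameters instead of 4. About 100 subjects with up to three visits each can support that.
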